## 6.3.3 Recording of adverse events

#### Time period for collection of adverse events

Adverse events will be collected from the volunteer's check-in to the study center on Day -1 of Period 1, throughout the treatment period and including the follow-up period.

Serious AEs will be recorded from the time of informed consent.

## Follow-up of unresolved adverse events

Any AEs that are unresolved at the volunteer's last AE assessment or other assessment/visit as appropriate in the study are followed up by the investigator for as long as medically indicated, but without further recording in the eCRF. AstraZeneca retains the right to request additional information for any volunteer with ongoing AE(s)/SAE(s) at the end of the study, if judged necessary.

#### Variables

The following variables will be collected for each AE:

- AE (verbatim)
- The date and time when the AE started and stopped
- Maximum intensity, rated according to the following scale:
  - Mild (awareness of sign or symptom, but easily tolerated)
  - Moderate (discomfort sufficient to cause interference with normal activities)
  - Severe (incapacitating, with inability to perform normal activities)
- Whether the AE is serious or not
- Investigator causality rating against the IP (yes or no)
- Action taken with regard to IP
- Whether AE caused volunteer's withdrawal from study (yes or no)
- Outcome

In addition, the following variables will be collected for SAEs:

- Date AE met criteria for serious AE
- Date Investigator became aware of serious AE
- AE is serious due to
- Date of hospitalisation
- Date of discharge
- Probable cause of death

- Date of death
- Autopsy performed
- Causality assessment in relation to Study procedure(s)
- Causality assessment in relation to Other medication
- Causality assessment in relation to Additional Study Drug
- Description of AE

It is important to distinguish between serious and severe AEs. Severity is a measure of intensity whereas seriousness is defined by the criteria in Section 6.3.2. An AE of severe intensity need not necessarily be considered serious. For example, nausea that persists for several hours may be considered severe nausea, but not a SAE. On the other hand, a stroke that results in only a limited degree of disability may be considered a mild stroke but would be a SAE.

#### **Causality collection**

The Investigator will assess causal relationship between Investigational Product and each Adverse Event, and answer 'yes' or 'no' to the question 'Do you consider that there is a reasonable possibility that the event may have been caused by the investigational product?'

For SAEs causal relationship will also be assessed for other medication and study procedures and additional study drug. Note that for SAEs that could be associated with any study procedure the causal relationship is implied as 'yes'.

A guide to the interpretation of the causality question is found in Appendix B to the Clinical Study Protocol.

#### Adverse Events based on signs and symptoms

All AEs spontaneously reported by the volunteer or reported in response to the open question from the study personnel: 'Have you had any health problems since the previous visit/you were last asked?', or revealed by observation will be collected and recorded in the eCRF. When collecting AEs, the recording of diagnoses is preferred (when possible) to recording a list of signs and symptoms. However, if a diagnosis is known and there are other signs or symptoms that are not generally part of the diagnosis, the diagnosis and each sign or symptom will be recorded separately.

#### Adverse Events based on examinations and tests

The results from protocol mandated laboratory tests and vital signs will be summarized in the CSR. Deterioration as compared to baseline in protocol-mandated laboratory values, vital signs or other safety variables should therefore only be reported as AEs if they fulfil any of the SAE criteria or are the reason for discontinuation of treatment with the IP.

If deterioration in a laboratory value/vital sign is associated with clinical signs and symptoms, the sign or symptom will be reported as an AE and the associated laboratory result/vital sign will be considered as additional information. Wherever possible the reporting investigator uses the clinical, rather than the laboratory term (eg, anemia versus low hemoglobin value). In the absence of clinical signs or symptoms, clinically relevant deteriorations in nonmandated parameters should be reported as AE(s).

Any new or aggravated clinically relevant abnormal medical finding at a physical examination as compared with the baseline assessment will be reported as an AE.

NB. Cases where a volunteer shows an AST or ALT  $\ge 3x$  upper limit of normal (ULN) or total bilirubin  $\ge 2x$  ULN may need to be reported as SAEs, please refer to Appendix D 'Actions required in cases of combined increase of Aminotransferase and Total Bilirubin – Hy's Law', for further instructions.

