## Study design

This is a Phase I, open-label, 2-period fixed sequence design study to evaluate the interaction of AZD9291 with omeprazole in approximately 50 healthy, adult male volunteers. The study will be performed at up to 2 sites in the USA.

Volunteers will receive Treatment A in Period 1 and Treatment B in Period 2. The dose of AZD9291 in Period 1 and the dose of AZD9291 in Period 2 will be separated by a washout of at least 21 days (the washout will not be more than 5 weeks).

Treatment A: On Days 1 through 4, omeprazole will be administered in the morning

after a 10-hour fast with 240 mL of water 1 hour before eating breakfast. On Day 5, omeprazole will be administered together with AZD9291 with 240 mL of water following an overnight fast of 10 hours and the

volunteers will remain fasting from food until 4 hours postdose.

Treatment B: Volunteers will receive AZD9291 in the morning on Day 1 with 240 mL

of water following an overnight fast of 10 hours. Volunteers will remain

fasting from food after dosing until 4 hours postdose.

The study will consist of up to 15 visits depending on whether the final pharmacokinetic (PK) sample of Period 1 is collected as the predose PK blood sample for Period 2 or whether a separate visit is required for the predose PK blood sample. The screening visit (Visit 1) will be conducted within 28 days of Visit 2. Following full written informed consent, healthy male volunteers will be enrolled into the study and screened for eligibility.

In Period 1 the volunteers will report to the clinic on Day -1 (the day prior to first dose of omeprazole) and remain resident until the 48-hour postdose (relative to AZD9291 administration on Day 5) monitoring and evaluations have been performed on Day 7. The volunteers will return to the clinic for outpatient visits on Days 8, 10, 12, 14 and 19. The Day 26 postdose assessments may be used as the Day -1 predose assessments for Period 2 if an exact 21-day washout is used between AZD9291 doses in Period 1 and Period 2. AZD9291 concentrations obtained over the first 72 hours in Period 1 will be evaluated to determine if exposure limit criteria for a given volunteer and/or a group of dosed volunteers are met or exceeded prior to AZD9291 administration in Period 2. Volunteer(s) exceeding PK exposure limits will be withdrawn.

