#### **Duration of treatment**

Period 1: On Days 1 through 4 volunteers will receive a single oral dose of 40 mg omeprazole. On Day 5, the volunteers will receive a single oral dose of 40 mg omeprazole together with a single oral dose of 80 mg AZD9291.

Period 2: On Day 1 volunteers will receive a single oral dose of 80 mg AZD9291.

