In Part A of the study (3 formulation comparison), 10/16 (62.5%) volunteers reported an AE during the 9-week duration of the study, with no SAEs, deaths or AEs leading to discontinuation. Only influenza was reported by more than 1 volunteer (n=3, 19%). No events were considered related to administration of AZD9291.

In Part B of the study (food effect), 6/16 (37.5%) volunteers reported an AE during the 6-week duration of the study, with no SAEs or deaths, and 1 AE leading to discontinuation after the first dosing period (alanine aminotransferase [ALT] increased). One further volunteer was lost to follow up after the first dosing period. Only upper respiratory tract infection was reported by more than 1 volunteer (n=2, 13%). Only 1 event of ALT increased was assessed as causally related to administration of AZD9291, which was an increase to a maximum value of 101 U/L on Day 15 after single dose of AZD9291 with no changes in aspartate aminotransferase (AST), bilirubin or alkaline phosphatase over this period. Other than the single event of ALT increased, no volunteers had any other clinically significant abnormal vital signs, clinical laboratory parameters or changes in electrocardiogram (ECG) parameters, including the QT interval corrected for heart rate (QTc).

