#### 1.3.3 Overall benefit-risk and ethical assessment

The potential for adverse drug reactions (ADRs) associated with AZD9291 is based on the AE profile of the class of drugs that inhibit the EGFR-signalling pathways and from observations from nonclinical and clinical studies of AZD9291. Specific volunteer selection criteria, appropriate safety assessments, and individual stopping criteria have been incorporated into the clinical program for AZD9291 based on the potential AEs and ADR profile. The risk to healthy volunteers is considered low given the limited exposure to 2 single doses of AZD9291 and the close safety monitoring planned during this study.

Further details are provided in the IB.

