# 2.3 Safety objective

To examine the safety and tolerability of AZD9291 in combination with omeprazole.

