#### 12.2.3 Safety and tolerability

Safety data include AEs, vital signs, physical examinations, ophthalmologic examination, electrocardiograms, and clinical laboratory assessments.

All safety data (scheduled and unscheduled) will be presented in the data listings. Continuous variables will be summarized using descriptive statistics (n, mean, SD, minimum, median, maximum) by treatment. Categorical variables will be summarized in frequency tables (frequency and proportion) by treatment.

All AEs that occur following the first dose of omeprazole in Period 1 will be included in the analyses of AEs, including episodes that occur during the wash-out period.

All available data from healthy volunteers in the safety analysis set will be included in the safety analyses.

All AEs will be collected for each healthy volunteer from Day -1, Treatment period 1 (Visit 2) until the follow-up visit (Visit 15). All SAEs will be collected for each healthy volunteer from the time when informed consent is obtained until the follow-up visit (Visit 15).

Adverse events will be listed for all healthy volunteers with AEs that occur before administration of the IP indicated on the listing. The number of AEs experienced following administration of the IP will be summarized in tables using the MedDRA (Version 13.0 or higher) system organ class and preferred term. These summary tables will also be produced with severity and causality of AEs added as additional classification factors. The number of AEs overall, SAEs, OAEs, AEs that lead to withdrawal, AEs of severe intensity, and causally-related AEs will be summarized. Any AE occurring postdose will be considered associated with the last dose of the IMP taken. Any AE occurring on Day -1, Treatment period 1 (Visit 2) will not be included in the summaries.

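### The AE rule for mandated tests depends on a later dose to stop, so it can work after AZD9291 + omeprazole (Period 1) but not after AZD9291 alone (Period 2)

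*Protocol*

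**What the plan says.** Section 6.3.3 (Adverse Events based on examinations and tests) starts from the premise that "The results from protocol mandated laboratory tests and vital signs will be summarized in the CSR". It concludes that deterioration from baseline in mandated laboratory values, vital signs or other safety variables should "only be reported as AEs if they fulfil any of the SAE criteria or are the reason for discontinuation of treatment with the IP". Accompanying signs or symptoms are AEs in their own right.

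The dosing is a fixed sequence: "Volunteers will receive Treatment A in Period 1 and Treatment B in Period 2". Section 1.3.3 describes "limited exposure to 2 single doses of AZD9291", and the synopsis places the last of these as follows: "Period 2: On Day 1 volunteers will receive a single oral dose of 80 mg AZD9291".

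Section 12.2.3 attributes each post-dose AE to the most recent dose. It summarises AEs by severity and causality, and says of safety data in general: "Categorical variables will be summarized in frequency tables (frequency and proportion) by treatment". The safety objective in section 2.3 is "To examine the safety and tolerability of AZD9291 in combination with omeprazole".

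Section 1.3.1 reports one AZD9291-related event in healthy volunteers, "an increase to a maximum value of 101 U/L on Day 15 after single dose of AZD9291". AST, bilirubin and alkaline phosphatase did not change. It was the AE that led to discontinuation after the first dosing period of Part B.

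**The concern.** Stopping the IP is a workable marker of importance when dosing is continuous, because at any time there is a next dose to withhold. Here there are two single doses in a fixed order. After the first, one dose can still be withheld. After the second, nothing is left to stop, although laboratory tests continue on Period 2 Days 3, 8, 15 and 22.

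The same non-serious, symptom-free change can therefore be an AE after the combination and cannot be one after AZD9291 alone. Since treatment and period coincide, the gap appears in the AE tables as a difference between treatments. It makes AZD9291 alone, the only within-study reference for the combination, look cleaner than it may be. Such an event also receives no investigator causality rating, because causality is collected only for AEs.

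**Working it through.** The protocol gives no figure on this point, so the check is a reading of its sections against each other, followed by an illustration of size.

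**Routes to an AE for a deterioration in a mandated test**

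| Route (section 6.3.3) | After Period 1 dose (combination) | After Period 2 dose (AZD9291 alone) |
|---|---|---|
| Meets an SAE criterion | open | open |
| Accompanied by signs or symptoms (these are the AE) | open | open |
| Is the reason for stopping the IP | open: one dose remains | closed: no dose remains |

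The test schedule is nearly symmetric and does not explain the difference. After AZD9291, laboratory tests fall at 48, 168 and 336 hours in both periods (Period 1 Days 7, 12 and 19; Period 2 Days 3, 8 and 15). A further test follows on Period 2 Day -1 for the first dose and on Period 2 Day 22 for the second. An ALT rise on Day 15 after dosing would be seen on Day 19 of Period 1, before the second dose at 21 days or later, or on Day 15 of Period 2, after the last dose.

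**Size**

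Inputs from section 1.3.1: Part A gave 16 × 3 = 48 doses and Part B gave 16 + 14 = 30, so 78 doses in 32 volunteers, with one ALT event judged related. From section 12.3: 50 enrolled and 40 evaluable, taken here as the numbers at risk in Periods 1 and 2.

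Assumptions: the true rate r per volunteer-period is the same in both periods, and every such event in Period 1 stops the second dose. Expected count = n × r. Probability of at least one = 1 − (1 − r)^n.

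| Assumed r | Period 1 AEs under the rule (n = 50) | Period 2 true events (n = 40) | P(at least one in Period 2) | Period 2 AEs under the rule |
|---|---|---|---|---|
| 1/78 = 1.3% | 0.6 | 0.5 | 40% | 0 |
| 1/32 = 3.1% | 1.6 | 1.3 | 72% | 0 |
| 1/16 = 6.3% | 3.1 | 2.5 | 92% | 0 |

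The Period 1 column is an upper bound for each rate, because an event that does not stop the second dose is not an AE there either. The zeros in the last column follow from the rule and do not depend on the assumed rate.

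**The case against.** The strongest reply is that the rule is deliberate and loses no data. Section 6.3.3 restricts AE reporting because these results are reported separately. Section 12.2.3 lists all scheduled and unscheduled safety data and summarises them by treatment. Section 11.1.1 adds change from baseline, and section 6.3.5 requires repeat sampling and monitoring of confirmed clinically significant laboratory values. Section 11.1.2 commits the sponsor to a review of laboratory, vital-sign and ECG data for other significant AEs, which are then counted. The safety objective concerns the combination, where the discontinuation route does work, and no inferential safety comparison is planned.

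Most of this stands. A reader might infer that the rule conceals the ALT signal in Period 2. It does not: the value would appear in the laboratory listings and summaries. A reader might also infer that an unscheduled ALT would be reportable while a scheduled one is not. The text does not support that, because the separate rule concerns parameters outside the mandated panel and ALT is in Table 3 whenever it is drawn. Nor can it be said that no Period 2 change could ever be reported, since the SAE and symptom routes remain open and the sponsor may classify a change as an other significant AE.

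These provisions still do not close the gap:

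- The sponsor's review takes place when the AE data are evaluated, its classification is discretionary, and the protocol attaches no investigator causality rating to it.
- The liver provisions may not catch an isolated ALT rise. The ULN is not given. 101 U/L reaches 3 × ULN only if the ULN is at most 101/3 = 33.7 U/L, and Appendix D's definition of a potential Hy's Law case also needs raised bilirubin, which the precedent lacked.
- The rule covers other safety variables, but its stated reason names only laboratory tests and vital signs. For ECGs, section 6.3.7 puts only a normal/abnormal result in the eCRF.

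**Conclusion.** The asymmetry is real and follows from the rule and the dosing sequence. It is confined to investigator-reported AEs that are non-serious and symptom-free, and so to the AE and causality tables. On the assumed rates, about 0.5 to 2.5 such events would be expected among 40 volunteers in Period 2, with none reported as an AE. The range rests on a single event at 20 mg carried over to 80 mg. Quoting only 2 to 3 events would use the Part B rate alone and ignore the 48 Part A doses without such an event.

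It would also go too far to say that the safety conclusion is biased. The analysis is descriptive, by-treatment AE counts are already confounded with period, and the underlying values are reported. The primary PK conclusion is unaffected. This is a cheap improvement worth making, not a flaw in the trial's main question.

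**What to change.** In section 6.3.3, add or substitute a criterion that does not depend on a remaining dose. For example, keep the two existing conditions and also report as an AE any deterioration in a mandated laboratory value, vital sign or ECG that the investigator confirms as clinically significant. For laboratory values, section 6.3.5 already produces that judgement through repeat sampling. For vital signs and ECGs the sentence should say who makes it. Apply the criterion identically in both periods and at follow-up, and leave any clinical threshold to the sponsor.

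The cost is one sentence and the matching eCRF completion instruction. There are no extra tests or visits. The downside is a few more non-serious AEs recorded.

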#### 6.3.4 Reporting of serious adverse events

All SAEs have to be reported, whether or not considered causally related to the investigational product, non investigational product, or to the study procedure(s). All SAEs will be recorded in the eCRF.

If any SAE occurs in the course of the study, then investigators or other site personnel inform appropriate AstraZeneca representatives immediately, or **no later than 24 hours** of when he or she becomes aware of it.

The designated AstraZeneca representative works with the investigator to ensure that all the necessary information is provided to the AstraZeneca Patient Safety data entry site within one calendar day of initial receipt for fatal and life threatening events and within five calendar days of initial receipt for all other SAEs.

For fatal or life-threatening adverse events where important or relevant information is missing, active follow-up is undertaken immediately. Investigators or other site personnel inform AstraZeneca representatives of any follow-up information on a previously reported SAE immediately, or **no later than 24 hours** of when he or she becomes aware of it.

#### 6.3.5 Laboratory safety assessment

Laboratory assessments will be taken at the times indicated in the Study Plans (Table 1 and Table 2). The date and time of collection of all laboratory tests will be recorded in the appropriate eCRF. Safety laboratory assessments will be performed at the site's local accredited laboratory, unless stated otherwise.

The laboratory variables to be measured are presented in Table 3.

Table 3 Laboratory safety variables

Clinical chemistry	Hematology	Urinalysis
Serum (S)-Albumin	Blood (B)-Hemoglobin	Urine (U)-Glucose
S-ALT	B-Hematocrit	U-Protein
S-AST	B-Erythrocyte	U-Blood
S-Alkaline phosphatase	B-Leukocyte	U-Specific gravity
S-Bilirubin, total	B-Leukocyte differential count (absolute)	U-pH
S-Calcium, total	Neutrophils	
S-Creatinine	Lymphocytes	
S-Glucose	Monocytes	
S-Magnesium	Basophils	
S-Potassium	Eosinophils	
S-Sodium	B-Platelet count	
S-Urea	B-Reticulocyte count	

ALT Alanine aminotransferase, AST Aspartate aminotransferase

Blood will be tested for HBsAg, antibodies to hepatitis C virus, and antibodies to HIV at the screening visit.

Urine will be tested at the screening visit and Day -1 of each treatment period (and randomly throughout the study at the discretion of the Investigator) for cotinine and the following drugs of abuse: methadone, cannabis, cocaine, benzodiazepines, amphetamine, methamphetamines (including ecstasy), opiates, barbiturates, phencyclidine, and tricyclic antidepressants. A breath test for alcohol will also be performed. The test will be performed at the study unit. If a volunteer tests positive for drugs of abuse, a retest may be performed, and they may be excluded from entering or continuing in the study, as judged by the Investigator.

If any laboratory values outside the laboratory's reference limits are suspected to be of clinical significance, as judged by the Investigator and/or AstraZeneca, the sampling will be repeated. Volunteers in whom the suspected clinical significance is confirmed at repeated sampling will either not be included or, if already included (started treatment), the deviating values will be monitored until normalization or for as long as the Investigator considers necessary.

**NB.** Cases where a volunteer shows an AST or ALT  $\ge 3x$  ULN or total bilirubin  $\ge 2x$  ULN may need to be reported as SAEs. Prompt reporting of cases meeting Hy's law criteria (via the SAE expedited reporting system) is required for compliance with regulatory guidelines. The investigator is responsible for, without delay, determining whether a patient meets potential Hy's law criteria. Please refer to Appendix D 'Actions required in cases of combined increase of Aminotransferase and Total Bilirubin – Hy's Law', for further instructions.

For blood volume see Section 7.1.

## 6.3.6 Physical examination

Physical examinations will be performed at the time points indicated in Table 1. A complete physical examination will be performed at screening and follow-up visit that includes an assessment of the following: general appearance, respiratory, cardiovascular, abdomen skin, head and neck (including ears, eyes, nose and throat), lymph nodes, thyroid, abdomen, musculoskeletal (including spine and extremities), and neurological systems. A brief physical examination (including general appearance, skin, abdomen, cardiovascular system, and lungs) to be performed at each admission.

